7.7.2.5 Determination of Subjects/Data for Analysis

All subjects who complete the defibrillation protocol will be included in the analysis.

7.7.3 Ancillary Objective #1: Appropriate and Inappropriate Shocks

Characterize appropriate and inappropriate shocks.

7.7.3.1 Hypothesis

There are no hypotheses for this objective. Spontaneous episodes receiving shocks will be summarized.

7.7.3.2 Performance Requirements and Endpoint Definition

Performance requirements are not pre-specified for this objective. The endpoint is defined as a shock delivered by the EV ICD. Spontaneous arrhythmic episodes resulting in a shock will be adjudicated to determine the underlying rhythm.

7.7.3.3 Rationale for Performance Criteria

Due to the minimal number of appropriate and inappropriate shocks expected for spontaneous arrhythmias, this objective is intended to only characterize device performance with regard to sensing ventricular arrhythmias and delivering shocks when the episode either does not self-terminate or is not terminated by ATP. There are no pre-specified performance criteria.

7.7.3.4 Analysis Methods

Results will be summarized in aggregate using descriptive statistics. All shocks delivered by the device for spontaneous arrhythmias will be partitioned by whether the treated rhythm was a VT/VF episode, and by the specific rhythm of the episode. Both the number of episodes and the number of subjects experiencing such episodes will be reported, as well as the energy delivered. Kaplan-Meier curves for time to first appropriate shock and time to first inappropriate shock may be provided to demonstrate shock incidence. Any instances of VT/VF terminated by ATP but also receiving a shock following ATP delivery will be reported.

7.7.3.5 Determination of Subjects/Data for Analysis

All subjects successfully implanted with an EV ICD having at least one device interrogation post-implant will be included in the analysis. At minimum, all episodes occurring by the date at which all implanted subjects have had the opportunity to be followed for 2 weeks post-implant will be included.

7.7.4 Ancillary Objective #2: Electrical Performance

Characterize electrical performance (pacing capture thresholds, pacing impedance, sensing amplitudes) over time.

7.7.4.1 Hypothesis

There are no hypotheses for this objective. Pacing capture performance, as well as pacing impedance and sensing amplitudes, will be summarized.

7.7.4.2 Performance Requirements and Endpoint Definition

Performance requirements are not pre-specified for this objective. The endpoints are defined as pacing capture threshold, pacing impedance, and sensing amplitude. The pacing testing will be performed at pre-hospital discharge, as well as visits at 2 weeks, 3- and 6-months post-implant and every 6 months thereafter.

7.7.4.3 Rationale for Performance Criteria

This objective is for the purpose of characterizing device performance with regard to achieving pacing capture and determining sensing performance over time. There are no pre-specified performance criteria.

7.7.4.4 Analysis Methods

Results will be summarized in aggregate using descriptive statistics. For each follow-up visit, the proportion of subjects undergoing pacing testing will be reported, as well as the proportion for whom capture is obtained. Mean impedance and R-wave amplitudes will also be reported at each follow-up for which the testing occurs (pre-hospital discharge, 2 weeks, 3- and 6-months post-implant, and every 6 months thereafter).

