8.5.6.1. Sensing Testing

Perform an RV sensing test. Set ICD RV sensing vector to Ring1-Ring2. Adjust sensing parameters to avoid T-wave oversensing, P-wave oversensing, or other oversensing. Once configured, perform the Sensing Test. Print the Sensing Test Report on the programmer to PDF or paper and store at site. Evaluate alternate sensing vectors as necessary. Program determined sensing settings.

The R-wave amplitude for sensing shall be greater than or equal to 1mV for the Ring1-Ring2 configuration.

If the R-wave amplitude is less than 1mV for the Ring1-Ring2 configuration after all troubleshooting attempts have been exhausted (refer to step 8 in Table 4), the EV ICD implant shall be abandoned and the implant of an alternative ICD system should be considered.

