8.5.8. Subject Exit for Incomplete Implant Visit

The subject shall be exited if any of the following occur during the implant visit:

- Incomplete Placement of Lead and/or Device – The EV ICD System is not fully implanted.

^{xvi} Lead revision is not permitted if the subject has resumed anticoagulation. Post-procedure anticoagulation should be resumed as soon as possible unless clinically contraindicated (e.g., effusion observed) in subjects who have had atrial fibrillation for ≥ 48 hours in duration prior to the implant procedure and who convert to sinus rhythm during defibrillation testing to diminish the risk of peri-procedural stroke.

Medtronic Business Restricted

- Incomplete Defibrillation Testing Protocol – The subject cannot complete the entire defibrillation testing protocol because they were not inducible or failed to induce a sufficient number of episodes.
 - Note: If the subject completes the initial implant procedure without completing the defibrillation testing protocol, the subject may be brought back prior to hospital discharge to complete the remainder of the defibrillation testing protocol, as outlined in Figure 7.
- Failure of Defibrillation Testing Protocol – The subject completes the defibrillation testing protocol but does not meet the criteria for success for defibrillation testing.
- Inadequate Sensing – The subject cannot achieve an R-wave ≥ 1 mV for the Ring1-Ring2 sensing vector after troubleshooting methods are exhausted.
- Inadequate SSVA Detection – The subject cannot achieve successful VF detection in a single SSVA episode in the Ring1-Ring2 configuration at a value greater than or equal to 0.2 mV after troubleshooting methods are exhausted.

If the subject does not complete the implant visit due to any of the reasons specified above, the EV ICD System shall be explanted, and the subject shall be followed and assessed for AEs through 30 days or until procedure or system related AEs have been resolved, at which point the subject can be exited (see section 8.19). If the subject receives an alternative system (e.g., S-ICD or TV ICD), any AEs related to the alternate system will be recorded during the course of subject participation, but will not be considered related to the EV ICD System.

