8.6.1. Sensing Testing

At the Pre-Hospital Discharge visit, perform the Sensing Test in the following postures:

- Sitting
- Supine
- Lying on left
- Lying on right

Print the Sensing Test Report to PDF or paper and send a copy of the report to Medtronic.

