8.7.6.1. Sensing Testing

At the 2-Week, 3-Month, 6-Month, and Long-Term follow up visits, perform the Sensing Test in a sitting posture. If necessary, sensing testing in additional postures may be performed. Print the Sensing Test Report to PDF or paper and send a copy of the report to Medtronic.

Medtronic Business Restricted

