7.7.4.5 Determination of Subjects/Data for Analysis

All subjects successfully implanted with an EV ICD having relevant data (pacing tests, impedance, sensing amplitudes) will be included in the analysis of that endpoint at that timepoint.

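### Ancillary Objective #2 concerns sensing over time, but SAP 7.7.4.4 names only a per-visit mean R-wave over whoever has data; a paired change from the sitting discharge reading would answer it better at almost no cost.

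*SAP*

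**What the plan says.** SAP 7.7.4.3 gives the purpose as characterizing the device "with regard to achieving pacing capture and determining sensing performance over time". SAP 7.7.4.4 (Analysis Methods) opens with a general promise of aggregate descriptive statistics. It then gives the proportions tested and captured for pacing, and adds: "Mean impedance and R-wave amplitudes will also be reported at each follow-up for which the testing occurs". Protocol 12.6.4 says the same.

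SAP 7.7.4.5 defines the set visit by visit: implanted subjects "having relevant data (pacing tests, impedance, sensing amplitudes) will be included in the analysis of that endpoint at that timepoint".

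The inputs come from the Protocol:

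- Section 8.6.1: "At the Pre-Hospital Discharge visit, perform the Sensing Test in the following postures". Four are listed: sitting, supine, left side and right side.
- Section 8.7.6.1, for 2 weeks and every later scheduled visit: "perform the Sensing Test in a sitting posture". Other postures are optional.
- Section 8.5.6.1, at implant: the test starts in Ring1-Ring2, then "Evaluate alternate sensing vectors as necessary. Program determined sensing settings". The discharge and follow-up sensing sections name no vector.
- The same section sets the implant acceptance limit: "The R-wave amplitude for sensing shall be greater than or equal to 1mV for the Ring1-Ring2 configuration". Section 8.5.8 makes failure to reach it a reason for exit.

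**The concern.** A question about change over time is best answered within subjects. The plan commits only to a cross-section at each visit, over a set that can differ from one visit to the next. This has two consequences.

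First, the mean can move because the set changed. A subject explanted without a replacement EV ICD is exited (Protocol 8.13), and withdrawn subjects are not replaced (Protocol 8.19). The report's timing adds to this. The Protocol synopsis (Statistics) starts the clinical study report once all implant-attempt subjects have completed the 2-week visit, while enrollment is expected to take about 5 months (Protocol 5.1). Any 3-month or later means available at that cut would come mainly from early enrollees.

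Second, a mean dilutes a marked fall in one subject. Deterioration of electrical performance is something the Protocol itself treats subject by subject (8.6.4 and 8.7.3).

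The posture gap affects the first comparison. If the discharge summary pooled or chose among four postures while 2 weeks used sitting, part of any difference could be postural.

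What is at stake is how well a descriptive ancillary table answers its own question. No hypothesis or performance criterion depends on it.

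**Working it through.** The plan states no R-wave mean, spread or expected change, so there is no figure to reproduce. The arithmetic below only shows how a mean behaves.

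**Inputs.** From the documents: n = 15 to 25 implanted subjects (SAP 6). Assumed: group mean m = 3 mV, one subject falling from b to e = 0.5 mV, all others unchanged.

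**1. One subject falls, same set.** Relative change in the mean = (e − b)/(n × m). Within-subject change = e/b − 1.

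| Start b (mV) | n = 15 | n = 25 | Subject's own change |
|---|---|---|---|
| 1.5 | −1.0/45 = −2.2% | −1.0/75 = −1.3% | −67% |
| 3 (average) | −2.5/45 = −5.6% | −2.5/75 = −3.3% | −83% |
| 6 | −5.5/45 = −12.2% | −5.5/75 = −7.3% | −92% |

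For an average subject (b = m) the result depends little on the assumed group mean. With m from 2 to 4 mV, the change is −5.0% to −5.8% (n = 15) and −3.0% to −3.5% (n = 25).

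**2. One subject leaves, nobody changes.** New mean = (n × m − value)/(n − 1).

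- A 1 mV subject leaves: (45 − 1)/14 = 3.14, or +4.8% (n = 15); (75 − 1)/24 = 3.08, or +2.8% (n = 25).
- A 6 mV subject leaves: (45 − 6)/14 = 2.79, or −7.1% (n = 15); (75 − 6)/24 = 2.875, or −4.2% (n = 25).

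The paired change is zero in every case. The effect of a changed set is about as large as one subject's fall and can go either way.

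**3. Fall followed by explant.** With n = 15 and everyone at 3 mV, one subject falls to 0.5 mV and is then exited. The successive means are 3.00, (14 × 3 + 0.5)/15 = 2.83, and 3.00. The series returns to its start.

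**4. Fall and departure between the same two visits.** One subject is at 1 mV and the rest at 3 mV. The 1 mV subject is not retested, and another falls to 0.5 mV.

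- n = 15: 43/15 = 2.867, then 39.5/14 = 2.821, or −1.6%.
- n = 25: 73/25 = 2.920, then 69.5/24 = 2.896, or −0.8%.

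**5. Posture.** Sitting is the only posture required both at discharge (8.6.1) and at later visits (8.7.6.1). A matched reading is therefore already collected; the SAP just does not say that it is the one summarized.

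**The case against.** The strongest reply is that little is lost. The mean is announced as an addition to unspecified descriptive statistics. The SAP's Introduction leaves reports free to add analyses, and SAP 7.3 puts all available data into listings and tabulations. With at most 25 subjects, a listing shows each trajectory. Missed visits and uncompleted testing are reported (SAP 7.1.1 and 7.1.2). Persistent sensing problems are an example of a device deficiency (Protocol 10.1.2), individual deficiencies are reported (SAP 7.8), and adverse events are listed case by case (SAP 7.7.8.4). All of this stands. A reader might infer that a subject's loss of sensing would go unreported; the documents do not support that. What the reply does not supply is a commitment to any within-subject summary.

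A second reply is that the report follows the 2-week visit, so the comparison that nearly everyone reaches is discharge to 2 weeks. That is fair, and it limits the set problem there. The problem is sharper for later visits and after an explant.

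Two further inferences go too far. One is that readings will come from different vectors: alternates may be evaluated, but Ring1-Ring2 is the starting and acceptance vector and no text shows that a mixture is expected. The other is that 1 mV is a follow-up standard. It governs acceptance at implant, "for the Ring1-Ring2 sensing vector after troubleshooting methods are exhausted", and SAP 7.7.4.3 sets no performance criteria.

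The discharge test may also be done at any time between implant and discharge (Protocol 8.6), so it is not a perfectly fixed baseline. It is still the first reading matched to follow-up on posture.

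**Conclusion.** The point holds as a minor improvement. The objective asks about change over time, and the only named R-wave statistic does not isolate change.

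The size rests wholly on assumed amplitudes. A fall to 0.5 mV with a group mean of 3 mV moves the mean by 1.3% to 12.2% across starting values of 1.5 to 6 mV and n of 15 to 25, and by 3.3% to 5.6% for a subject who starts at the mean. A reader might take about 3% to 6% as a property of this plan. It is not: it needs an average starting amplitude, a large fall, and all 15 to 25 subjects measured. That any mean dilutes one value is general; what is specific here is pairing such a mean with an over-time purpose and a visit-by-visit set.

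The open choice of discharge posture is a real but small gap. A vector mismatch is only a possibility. The primary safety and efficacy results are untouched.

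**What to change.** In SAP 7.7.4.4:

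1. Keep the mean R-wave at each visit, and state that it uses the sitting reading at every visit, including discharge, and in which sensing vector.
2. Report n, minimum and maximum alongside it.
3. Add the within-subject change from the sitting discharge value, in the same sensing vector, for subjects with both values, and give that n.

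Optionally, show the number below 1 mV in Ring1-Ring2 and the number not tested in that vector. If shown, label it as descriptive, taken from the implant acceptance limit, and not a performance criterion.

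The cost is a few table rows and a smaller n for the paired summary where a reading or the matching vector is missing. No new data are needed, because the sitting tests are already required. A Protocol amendment should not be needed: Protocol 12.1 requires one only when a principal feature changes, and lets other analysis changes be described and justified in the clinical study report.

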7.7.4.5 Determination of Subjects/Data for Analysis

All subjects successfully implanted with an EV ICD having relevant data (pacing tests, impedance, sensing amplitudes) will be included in the analysis of that endpoint at that timepoint.

7.7.5 Ancillary Objective #3: Extracardiac Pacing Sensation

Characterize extracardiac pacing sensation.

7.7.5.1 Hypothesis

There are no hypotheses for this objective.

7.7.5.2 Performance Requirements and Endpoint Definition

Performance requirements are not pre-specified for this objective. The endpoint will be defined as whether pacing therapies were programmed OFF due to pacing sensation.

7.7.5.3 Rationale for Performance Criteria

There are no pre-specified performance criteria; pacing sensation at follow-up will be summarized and reported.

7.7.5.4 Analysis Methods

Results will be summarized in aggregate using descriptive statistics. Descriptive statistics will be used to summarize distribution among the subjects who completed each follow-up visit, and whether pacing therapies, specifically ATP, were programmed OFF due to the subject reporting pacing sensation. This objective will be analyzed using data from the pre-hospital discharge, 2 weeks, 3- and 6-month, and long-term visits.

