8.8. Unscheduled Visits

An Unscheduled follow-up visit is defined as any non-standard of care visit by the subject to the investigative study site due to the EV ICD System between CIP-required visits.

If an Unscheduled Visit occurs:

- Document any adverse events and/or device deficiencies on the associated eCRFs, as applicable.
- Where possible, initial (beginning of the visit) and final (end of the visit) device interrogation data should be collected via a save-to-media file (see section 8.10).
- If electrical testing is conducted, print the Testing Reports to PDF or paper and send a copy of the reports to Medtronic.

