7.7.5.5 Determination of Subjects/Data for Analysis

For each visit (e.g., PHD, 2 weeks), all subjects successfully implanted with an EV ICD who complete that visit will be included in the analysis.

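### Objective #3 counts ATP switched OFF for sensation only at scheduled visits, so an OFF setting reversed, or followed by explant and exit, before the next one is missed

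*SAP*

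**What the plan says.** **Objective #3.** SAP 7.7.5.2 sets the endpoint with no visit restriction: "The endpoint will be defined as whether pacing therapies were programmed OFF due to pacing sensation". SAP 7.7.5.4 then restricts the data: "This objective will be analyzed using data from the pre-hospital discharge, 2 weeks, 3- and 6-month, and long-term visits". SAP 7.7.5.5 sets the denominator visit by visit: "all subjects successfully implanted with an EV ICD who complete that visit will be included in the analysis". CIP 12.7.2, 12.7.4 and 12.7.5 match.

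**Objective #2.** SAP 7.7.4.4 has impedance and R-wave amplitude "reported at each follow-up for which the testing occurs (pre-hospital discharge, 2 weeks, 3- and 6-months post-implant, and every 6 months thereafter"). SAP 7.7.4.5 places each subject's data by endpoint and visit: they "will be included in the analysis of that endpoint at that timepoint".

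**Off-schedule data.** CIP 8.8 defines an unscheduled visit as "any non-standard of care visit by the subject to the investigative study site due to the EV ICD System between CIP-required visits". It adds: "If electrical testing is conducted, print the Testing Reports to PDF or paper and send a copy of the reports to Medtronic". CIP Table 2 schedules save-to-media files at unscheduled and system-modification visits and marks electrical testing at unscheduled visits as optional. CIP 8.13 requires an interrogation file before a revision, asks the physician to consider an electrical evaluation, and repeats the pre-hospital discharge (PHD) data collection after a lead is replaced or repositioned. A subject explanted without a replacement EV ICD is exited.

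**The concern.** An unscheduled visit is, by definition, prompted by the system. It is a natural place for a subject troubled by pacing sensation to have ATP reprogrammed. Objective #3 does not list that visit type as a data source, and no SAP rule assigns its data to a scheduled visit. The subjects most likely to be affected are thus the ones the summary can miss, and the error runs one way: a missed subject makes the sensation rate look better.

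The restriction is particular to Objectives #2 and #3. Objectives #1, #4, #5 and #6 (SAP 7.7.3.5, 7.7.6.5, 7.7.7.5 and 7.7.8.5) take in all episodes, pacing instances or events up to a calendar date, whatever the visit type.

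At stake is a descriptive rate in a small study. No hypothesis or performance criterion depends on it.

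**Working it through.** The plan states no rate, precision or sample-size figure for Objective #2 or #3, so there is no planned figure to reproduce. The check is to follow possible sequences through the text.

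**Inputs.** Data source: SAP 7.7.5.4. Denominator: SAP 7.7.5.5. Exit after explant: CIP 8.13. Number implanted: about 15 and up to 25 (SAP 6).

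**Step 1. Sequences under Objective #3.**

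| Sequence for one subject | By-visit summary as written | Cumulative any-visit count |
|---|---|---|
| ATP switched OFF for sensation at a scheduled visit | Counted | Counted |
| Switched OFF at an unscheduled or system-modification visit, still OFF at the next completed scheduled visit | Counted if the table shows the current setting; the SAP does not say whether it shows setting or change | Counted |
| Switched OFF off-schedule, back ON before the next scheduled visit | Not counted | Counted |
| Switched OFF off-schedule, then explanted without replacement and exited before the next scheduled visit | Not counted, and absent from later denominators | Counted, and kept in the denominator |

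The third and fourth rows are the gap.

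**Step 2. Weight of one subject.** If k subjects follow the third or fourth row among n implanted, the ever-OFF proportion is understated by k/n. With k = 1:

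- n = 15: 1/15 = 6.7 percentage points
- n = 25: 1/25 = 4.0 percentage points

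This is the weight of one missed subject. It is not an expected bias, because the documents give no frequency for k.

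**Step 3. Objective #2.** A mean at a fixed visit describes performance at that visit, and a reading taken after a correction is a true reading for that visit. What has no named place is the reading that led to the correction.

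For scale only, CIP Appendix D reports 10 lead dislodgements among the major complications in 316 pivotal-study implant attempts through 182 days. Assume one per subject and the same rate here: p = 10/316 = 0.0316.

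- Expected number, n × p: 15 × 0.0316 = 0.47; 25 × 0.0316 = 0.79
- Chance of at least one, 1 − (1 − p)^n: 38% for n = 15; 55% for n = 25

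A listing of off-schedule readings from this cause would be empty or very short. These figures say nothing about how often sensation leads to ATP being switched OFF.

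**The case against.** The other side has a good deal of substance.

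- **Persistence.** The endpoint can be read as a programming state. An OFF setting still in place at the next scheduled visit can be counted there, and a persisting loss of capture or sensing can be measured again. This stands, and it narrows the gap to the two sequences above.
- **Other routes to the report.** SAP 7.3 puts all available data into listings and tabulations, and SAP 3 allows further analyses. SAP 7.7.8.4 lists individual adverse events and SAP 7.8 reports device deficiencies, whatever the visit type. CIP 8.8 has adverse events documented at unscheduled visits, and CIP Table 9 names extracardiac stimulation as a potential event. This stands in part. The general sentences do not override a named data source or give a counting rule, and neither listing yields an ATP-OFF rate. CIP 8.6.3, on PHD testing, does exclude sensation observed during testing from reportable adverse events. Sensation that brings a subject in between visits is not obviously covered by that exclusion.
- **Frequency.** Sensation may mostly be met during scheduled pacing tests, so the pathway may be rare. The documents do not settle this.
- **Availability.** Off-schedule testing is optional and unscheduled-visit files are collected only where feasible. The case report forms are under separate cover (CIP Appendix A), so it is not shown that the reason for switching ATP OFF is recorded. This stands and belongs in the fix.

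A reader might go further and infer that off-schedule findings are lost altogether, or that the Objective #2 means are biased. The documents do not support either, for the reasons in the first two items and in Step 3. A reader might also take the visit windows in CIP Table 7 as a measure of loss. From day 14 to day 395 they cover 37 + 31 + 61 + 61 = 190 of 382 days, about half. The arithmetic is right, but days outside a window do not measure lost data when a setting persists or can be tested again.

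**Conclusion.** The point holds for Objective #3 in a narrow form. Followed as written, the summary does not count a subject whose ATP is switched OFF for sensation at an unscheduled or system-modification visit and who, before the next scheduled visit, has it switched back ON or is explanted and exits. The rate can therefore be understated, by 6.7 points per subject at n = 15 or 4.0 at n = 25. Whether any subject will follow such a course cannot be estimated from the documents. For a persisting OFF setting, the conclusion assumes that the by-visit table reports current status; the SAP should say so.

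For Objective #2 the by-visit means are acceptable, and only an explicit listing is wanting. Both objectives are ancillary, descriptive and without performance criteria, and no primary result is affected. Severity is low; the change is worth making because it is cheap.

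**What to change.** 1. **SAP 7.7.5.4.** Keep the by-visit table and state that it shows current programming status at that visit. Add a cumulative count of subjects whose ATP was ever switched OFF for sensation at any visit type (scheduled, unscheduled or system modification), with all successfully implanted subjects as the denominator. Do not carry OFF forward into the by-visit figures, since that would show a subject as OFF after ATP is back ON.
2. **Data source.** Confirm that the electronic case report form or the adverse event form records the reason for switching ATP OFF at off-schedule visits. If neither does, add the item or state the limitation.
3. **SAP 7.7.4.4.** Leave the by-visit summaries unchanged. Add a listing, by day post-implant, of any capture, impedance and R-wave readings available from unscheduled and pre-modification tests. This makes the general rule in SAP 7.3 explicit.
4. **Consistency.** Align CIP 12.7.4, or describe and justify the change in the clinical study report as CIP 12.1 provides.

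The cost is one extra count, one short listing, a check of the forms and possibly one added form item. The sensation rate may come out slightly less favourable.
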